5.2. Expected Risks

The additional sequences are no more than 12 minutes and do not place individuals at any increased risk.

6. UNANTICIPATED CONCERNS

6.1.1. Unanticipated Adverse Device Effect (UADE)

The investigational device exemption (IDE) regulations define an unanticipated adverse device effect (UADE) as “any serious adverse effect on health or safety or any life-threatening problem or death caused by, or associated with, a device, if that effect, problem, or death was not previously identified in nature, severity, or degree of incidence in the investigational plan or application (including a supplementary plan or application), or any other unanticipated serious problem associated with a device that relates to the rights, safety, or welfare of subjects” (21 CFR 812.3(s)).

6.1.2. Unanticipated Problems (UP)

As defined by UNC's IRB, unanticipated problems involving risks to study subjects refers to any incident, experience, or outcome that:

- Is unexpected (in terms of nature, severity, or frequency) given (a) the research procedures that are described in the protocol-related documents, such as the IRB-approved research protocol and informed consent document; and (b) the characteristics of the subject population being studied;
- Is related or possibly related to a subject's participation in the research; and
- Suggests that the research places subjects or others at a greater risk of harm (including physical, psychological, economic, or social harm) related to the research than was previously known or recognized.

6.1.3. Reporting

6.1.4. UADEs

UADEs must be reported by the clinical investigator to the sponsor and the reviewing IRB, as described below:

For this device study, investigators are required to submit a report of a UADE to the FDA, the manufacturer of the device and the UNC IRB as soon as possible, but in no event later than 10 working days after the investigator first learns of the event (§ 812.150(a)(1)), using the MedWatch Form 3500A. Sponsors must immediately conduct an evaluation of a UADE and must report the results of the evaluation to FDA, the UNC IRB, and participating investigators within 10 working days after the sponsor first receives notice of the effect (§§ 812.46(b), 812.150(b)(1)).

For this device study, we will submit a report of a UADE to the manufacturer and the IRB as soon as possible, but no later than 10 working days after the investigators first learn of the event.

6.1.5. UP

Any events that meet the criteria for "Unanticipated Problems" as defined by UNC's IRB must be reported by the Study Coordinator using the IRB's web-based reporting system.

Any unanticipated problem that occurs during the conduct of this study and that meets **at least** the first two criteria listed in section 8.2 must be reported to the UNC IRB using the IRB's web-based reporting system.

6.2. Data and Safety Monitoring Plan

The Principal Investigator will provide continuous monitoring of patient safety in this trial with periodic reporting to the Data and Safety Monitoring Committee (DSMC).

Meetings/teleconferences will be held at a frequency dependent on study accrual, and in consultation with the study Biostatistician. These meetings will include the investigators as well as protocol nurses, clinical research associates, regulatory associates, data managers, biostatisticians, and any other relevant personnel the principal investigators may deem appropriate. At these meetings, the research team will discuss all issues relevant to study progress, including enrollment, safety, regulatory, data collection, etc.

The team will produce summaries or minutes of these meetings. These summaries will be available for inspection when requested by any of the regulatory bodies charged with the safety of human subjects and the integrity of data including, but not limited to, the oversight (Office of Human Research Ethics (OHRE) Biomedical IRB, the Oncology Protocol Review Committee (PRC) or the North Carolina TraCS Institute Data and Safety Monitoring Board (DSMB).

The UNC LCCC Data and Safety Monitoring Committee (DSMC) will review the study on a regular (quarterly to annually) basis, with the frequency of review based on risk and complexity as determined by the UNC Protocol Review Committee. The UNC PI will be responsible for submitting the following information for review: 1) safety and accrual data including the number of study participants treated; 2) significant developments reported in the literature that may affect the safety of participants or the ethics of the study; 3) preliminary response data; and 4) summaries of team meetings that have occurred since the last report. Findings of the DSMC review will be disseminated by memo to the UNC PI, PRC, and the UNC IRB and DSMB.

7. STATISTICAL CONSIDERATIONS

7.1. Study Design/Study Endpoints

This prospective single instituted study will enroll about 30 patients that are scheduled to have screening breast MRI study to have the investigational MR sequences in the same study schedule adding no more than 12 minutes scanning time. The study ends when enough number of patients collected and analyzed.

7.2. Sample Size and Accrual

Our objective is to approximate the reliability for the 3D MR Fingerprinting method, which can be quantified by the Intraclass Correlation Coefficients (ICC). Given the previous preliminary experience of [name] using 3T MRI in Case Western Hospital, the ICC for T1 and T2 MRF are 0.82 and 0.875, respectively, with 12 healthy pre-menopausal volunteers scanned twice within 7-15 days. Suppose we choose 30 normal subjects and select 2 breast tissue locations for both left and right breasts for each subject to obtain 120 breast tissue images. For each breast tissue image we have two measurements using the MRF. For T1, our hypothesis test is **$H_0: ICC = 0.82$ vs. $H_1: ICC < 0.82$** , and the power will be 0.858 with significance level $\alpha = 0.05$ according to [17, 18], if the true

ICC=0.72; the power will be 0.935 with significance level $\alpha = 0.05$, if the true ICC=0.70. For T2 image, if we test $H_0: ICC = 0.875$ vs. $H_1: ICC < 0.875$, the power will be 0.969 with significance level $\alpha = 0.05$, if the true ICC=0.775; the power will be 0.873 with significance level $\alpha = 0.05$, if the true ICC=0.80; the power will be 0.749 with significance level $\alpha = 0.05$, if the true ICC=0.815. Therefore, we propose 30 normal control subjects with measurements twice, to measure the reliability of the 3D MRF technology. The measurement will be evaluated for both before and after contrast enhancement.

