3. PATIENT ELIGIBILITY

3.1. Inclusion Criteria

[figure not shown]
- 3.1.1.** English-speaking patients
- 3.1.2.** Ages 18 to 99 years old
- 3.1.3.** Scheduled to undergo a screening breast MRI study
- 3.1.4.** Capable and willing to provide signed informed consent

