4. STUDY PLAN

4.1. STUDY SCHEMA

4.2. Study Procedures

The patients will have a set of additional research scan of no more than 12 minutes scan time (MRF) within their primary screening breast MRI study. Patient will receive their standard clinical care as usual. No follow up needed for this observational study.

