5. INVESTIGATIONAL DEVICE

5.1. Investigational Device Description

Investigational sequences will be developed at UNC. The proposed study will be performed on the 1.5T MR scanners: (1) Main campus Siemens Avanto, Invivo 7-channel; (2) Out-patient Imaging center: Siemens Magnetom Aera, Sentinel Coil. The scanners are FDA approved and all new sequenced

possess the same safeguards as standard (FDA approved) clinical sequences to prevent harm to subjects. The study does not need any contrast administration unless it is required for standard clinical examination. For each consented subject, the additional scans will add no more than 12 minutes to the total scanning time. That is 6 minutes with two MRF sequences (3 minutes on each MRF sequence) pre-contrast enhancement phase and 6 minutes with two MRF sequences at the end of post contrast enhancement phase.

The investigational MR protocol will be implemented on the existing MR scanners without any modifications to the existing, FDA approved machine, equipment, or safety standards. Patients will receive their standard of care imaging. In addition, they will receive the research sequence. The additional sequences will be performed at no cost to the patient other than a small increase in the amount of time spent inside the MR scanner. The additional sequences are no more than 12 minutes and do not place individuals at any increased risk.

The research images will not be interpreted or analyzed for clinical decisions related to the patient. As such, this study will request that the IRB make a determination that this study is no greater than minimal risk. This study meets all the requirements for an NSR determination including:

- The device will not be implanted.
- The device is not intended to support or sustain human life.
- The device is not being used of substantial importance in diagnosing, curing, mitigating, or treating disease.
- The device does not present a potential for serious risk to health, safety, or welfare of a subject.

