7.3. Data Analysis Plans

We will calculate the inter-subject and intra-subject variability and estimate the ICC and its confidence interval for both the T1 and T2 values of normal breast tissue between the two MRF sequences at pre-contrast phase, and the post contrast delayed phase, respectively, to establish the parameter stability between scan times. We will also estimate the T1, T2 value change from pre to post contrast enhancement phases to establish the baseline value of normal breast parenchyma at pre and post contrast enhancement phases. We will compare the results with previous literature [19] and use independent two sample t-test to check if significant difference between MRF and with results in previous literature does not exist.

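### Section 7.2 sizes the study on an ICC test against 3T, 7-15 day benchmarks with 120 independent locations, while Section 7.3 plans a same-session 1.5T ICC whose confidence interval has no stated precision

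*Combined protocol and SAP*

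**What the plan says.** Section 7.2 sets two one-sided tests, ICC = 0.82 against ICC < 0.82 for T1 and ICC = 0.875 against ICC < 0.875 for T2. Both nulls come from earlier 3T work at another hospital, "with 12 healthy pre-menopausal volunteers scanned twice within 7-15 days". The number of units comes from the plan to "select 2 breast tissue locations for both left and right breasts for each subject to obtain 120 breast tissue images", each measured twice. Section 7.2 quotes powers of 0.858 and 0.935 for T1 (true ICC 0.72 and 0.70), and 0.969, 0.873 and 0.749 for T2 (true ICC 0.775, 0.80 and 0.815). It concludes that 30 subjects measured twice are proposed "to measure the reliability of the 3D MRF technology".

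The measurements in this trial are different. Section 5.1 states "The proposed study will be performed on the 1.5T MR scanners" and describes the repeats: "That is 6 minutes with two MRF sequences (3 minutes on each MRF sequence) pre-contrast enhancement phase", with a second such pair at the end of the same exam. Section 3.1 admits "Ages 18 to 99 years old", and Section 4.2 says "No follow up needed for this observational study". Section 7.3 will "estimate the ICC and its confidence interval for both the T1 and T2 values of normal breast tissue between the two MRF sequences", separately before and after contrast. It does not repeat the hypothesis test of Section 7.2.

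**The concern.** The benchmark and the quantity tested differ in retest interval, field strength and population. In an ICC from scans 7-15 days apart, change between visits counts as error. Two scans minutes apart share that change, so it does not count as error between them. On this factor alone the same-session ICC tends to be higher. Field strength and population could move it either way. No section adjusts the nulls or justifies carrying them over.

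The test can only detect an ICC below the benchmark, so the result most likely to be read as reassuring is a non-rejection. That would not show that the pilot's reliability had been matched.

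Two further points do not depend on the benchmark. The power calculation treats 120 locations in 30 women as 120 independent units. It also justifies a test that the analysis plan does not list, and says nothing about the width of the interval that the plan does list. If that interval is computed as though there were 120 independent units, it will be too narrow.

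**Working it through.** **1. The plan's own figures.** Inputs from Section 7.2: N = 120 units, k = 2 measurements, one-sided alpha 0.05. With k = 2, let θ = (1 + ICC)/(1 − ICC). The usual approximation is

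power = Φ( √[(N−1)(k−1)/(2k)] × ln(θ₀/θ₁) − 1.645 ), where √(119/4) = 5.454.

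| | θ₀ | θ₁ | ln(θ₀/θ₁) | z | Power | Stated | Exact F |
|---|---|---|---|---|---|---|---|
| T1, 0.72 | 10.111 | 6.143 | 0.498 | 1.073 | 0.858 | 0.858 | 0.857 |
| T1, 0.70 | 10.111 | 5.667 | 0.579 | 1.513 | 0.935 | 0.935 | 0.934 |
| T2, 0.775 | 15 | 7.889 | 0.643 | 1.860 | 0.969 | 0.969 | 0.968 |
| T2, 0.80 | 15 | 9 | 0.511 | 1.141 | 0.873 | 0.873 | 0.872 |
| T2, 0.815 | 15 | 9.811 | 0.425 | 0.671 | 0.749 | 0.749 | 0.748 |

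All five reproduce, so there is no arithmetic error. They apply to the ICC of the two scans actually taken, with 120 independent units. At the other extreme, N = 30, the same formula gives 0.381 (T1, 0.72) and 0.394 (T2, 0.80).

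**2. Benchmark against target.**

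| | Benchmark (7.2) | This trial (3.1, 4.2, 5.1, 7.3) |
|---|---|---|
| Field | 3T | 1.5T |
| Interval | 7-15 days | same session, two 3-minute scans |
| Subjects | 12 healthy pre-menopausal volunteers | screening patients aged 18 to 99 |
| Repeat visit | yes | none |

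If a share f of the 7-15 day error variance arises between visits, and nothing else differs, then same-session ICC = ICC + f(1 − ICC). The documents give no value for f, and field and population may act in the opposite direction. Purely as illustration, f = 0.10 turns a 7-15 day T1 ICC of 0.72 into 0.748, and f = 0.25 turns it into 0.79. The chance of rejecting 0.82 is then 0.66 or 0.24. For a T2 ICC of 0.80 the chances of rejecting 0.875 are 0.69 and 0.28. The conclusion does not rest on these figures.

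**3. Precision of the planned interval.** F-method 95% limits: θ_L = θ / F₀.₉₇₅(N−1, N), θ_U = θ × F₀.₉₇₅(N, N−1), and ICC = (θ−1)/(θ+1). The F quantiles are 2.083 and 2.092 for N = 30, and 1.434 for both at N = 120.

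| ICC | Units | θ_L, θ_U | 95% CI | Width |
|---|---|---|---|---|
| 0.82 | 30 | 4.855, 21.16 | 0.658-0.910 | 0.251 |
| 0.82 | 120 | 7.053, 14.50 | 0.752-0.871 | 0.119 |
| 0.875 | 30 | 7.202, 31.38 | 0.756-0.938 | 0.182 |
| 0.875 | 120 | 10.46, 21.51 | 0.826-0.911 | 0.086 |

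**4. Where clustering puts the trial between these bounds.** Simulation of 30 women × 4 locations × 2 repeats with a one-way ICC. The sharing fractions are assumptions, because the documents give none. The ranges are the 2.5 to 97.5 percentiles of the estimated ICC. Coverage is that of a 95% interval computed as if there were 120 independent units.

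| Shared within a woman | Range at 0.82 | Range at 0.875 | Coverage |
|---|---|---|---|
| Half of between-location variance, error independent | 0.737-0.875 | 0.814-0.914 | about 91% |
| Half of between-location variance and half of error | 0.723-0.883 | 0.804-0.919 | about 87% |

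The second row is equivalent to about 69 independent units. If all of both variances were shared, the ranges would be 0.652-0.908 and 0.749-0.937, or about 30 units.

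**The case against.** The strongest reply is that the trial draws no conclusion about visits. Section 7.3 speaks only of stability between scan times within each phase. No follow-up is planned, and no passage says what follows from failing to reject. Section 7.3 does not even repeat the test, so the benchmark mainly serves to size the study, and pilot values are an ordinary source for that. Section 7.2 discloses where its values come from, and Section 7.3 already defines the ICC within phase. Section 1.5 calls this a feasibility study. The primary objective in Section 2.1 is T1 and T2 baselines, and the primary endpoint in Section 2.2 does not name the ICC.

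Most of this stands, and it limits how far the point goes. A reader might infer that the protocol claims reliability across visits, or that its real power is only 0.24 to 0.69. The documents support neither. There is no cross-visit claim, and those powers depend on assumed between-visit shares with field strength and population held fixed, when the net direction is unknown.

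The reply does not rescue the sample-size argument. Section 7.2 states a formal hypothesis test, and its power is the only justification given for 30 women. It names reliability as the objective without an interval, beside a 7-15 day figure, so readers will set the result against that figure. Clustering and interval width would need attention even with a well-matched benchmark.

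**Conclusion.** The point holds as a mismatch between the sample-size justification and the planned analysis. It is not an error of arithmetic. The nulls describe a different quantity from the one estimated, so a non-rejection cannot be read as reproducing the pilot's reliability. How far off the benchmark is, and in which direction, cannot be settled from the documents.

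The stated powers are best-case values that assume independent locations. For the interval actually planned, 30 women give a 95% CI width between 0.119 and 0.251 at an ICC of 0.82, and between 0.086 and 0.182 at 0.875. The position within those bounds depends on how strongly the four locations in a woman are correlated. Under the two partial-sharing assumptions shown, an interval that ignores this would cover about 91% or 87% instead of 95%.

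The data remain usable. The justification, the interval method and the scope of the conclusion should be corrected.

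**What to change.** In Section 7.2, stop using 0.82 and 0.875 as test nulls and keep them as planning values only. Justify 30 women by the expected 95% CI width for the ICC, shown between the bounds of 30 and 120 independent units tabulated above.

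In Section 7.3, compute the ICC interval with a method that accounts for locations nested within breast and woman, such as a mixed model or a bootstrap that resamples women. State that the ICC measures within-session repeatability at 1.5T, before and after contrast separately, and that visit-to-visit reproducibility is not assessed.

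Optionally, report the within-subject SD between the two repeats and the repeatability coefficient, 1.96 × √2 × SD = 2.77 × SD, for T1 and T2. Section 7.3 already plans the intra-subject variability from which this follows.

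The cost is a rewritten paragraph and a few sentences. The power statement gives way to a less favourable precision statement, and the claim becomes narrower. No patients, visits or scans are added.

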1.5. Rationale

This is a feasibility study of the use of the additional MRF scanning sequence with a total of 12 minutes scanning time to our clinical screening breast DCE MRI examination before contrast medium injection and at the end of scan. This additional scanning sequence may provide faster and better quantitative tissue characterization comparing to conventional MR sequences. There is no investigational contrast agent in this study. We propose that the additional MRF sequence may provide faster and more accurate tissue characteristics imaging for clinical evaluation of breast tissue. Patients will be enrolled in with scheduled high risk screening DCE MRI (n=30). The MR imaging will be performed in the clinical 1.5T MR scanners in UNC as normally done for the patients MRI schedule. We only add an additional MRF sequence within the MRI exam just prior to the contrast enhancement scan.

Quantitative measurement of the breast tissue will be performed after the MR exam. The ROI of normal breast parenchyma was recorded. The ROI will be saved and encoded to the T1 map, T2 map in MRF, T1 weighted imaging, T2 weighted imaging. A large variety of imaging ROI-based quantitative measures will be calculated among normal glands in bilateral breasts to evaluate different ROI characteristics among different patients and between bilateral breasts in each patient.

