2. STUDY OBJECTIVES

2.1. Primary Objectives

The purpose of this study is to evaluate the novel quantitative MRI techniques, namely MR Fingerprinting (MRF), in clinical studies to establish the T1 and T2 value baselines of normal glandular tissue.

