2.2. Primary Endpoint

The normal breast tissue T1, T2 value will be used to compare between sides in same patient and among the different patients and between two MRF sequences in pre-contrast phase and post contrast enhancement phase and also the differences between pre and post contrast enhancement phases.

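### The five ICC powers in section 7.2 treat 120 locations as independent, but they are four locations in each of 30 women, and section 7.3 makes no allowance for this

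*Combined protocol and SAP*

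**What the plan says.** Section 7.2 plans to "select 2 breast tissue locations for both left and right breasts for each subject to obtain 120 breast tissue images". That is two locations in each of two breasts, four per woman, in 30 women. Each location is measured twice. Section 5.1 shows where the pair comes from: "6 minutes with two MRF sequences (3 minutes on each MRF sequence) pre-contrast enhancement phase", and the same again at the end of the post-contrast phase.

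On this basis 7.2 gives five powers for one-sided tests against a lower ICC. For T1 (null 0.82) it says "the power will be 0.858 with significance level" 0.05 when the true ICC is 0.72, and gives 0.935 at 0.70. For T2 (null 0.875) it gives 0.969, 0.873 and 0.749 at true ICCs of 0.775, 0.80 and 0.815. It then concludes: "we propose 30 normal control subjects with measurements twice, to measure the reliability of the 3D MRF technology".

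The analysis in 7.3 is: "We will calculate the inter-subject and intra-subject variability and estimate the ICC and its confidence interval", for T1 and T2 in each contrast phase. It names no ICC model, interval method or confidence level, and does not say how the four locations per woman enter.

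Other sections recognise that the data are nested. Section 2.2 intends to "compare between sides in same patient and among the different patients", and section 1.5 to "evaluate different ROI characteristics among different patients and between bilateral breasts in each patient".

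**The concern.** A test on 120 units has the stated power only if the 120 true values are independent. Here they come in groups of four from the same woman. A plan that sets out to compare women with each other, and sides within a woman, can hardly take it for granted that a woman's locations are unrelated. Section 7.2 nevertheless uses a correlation of zero, the most favourable value, without saying so.

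Two things are at stake. The choice of 30 women rests on powers that may be overstated. And the ICC interval, which is what 7.3 will actually report, will be too narrow if it is computed on 120 units.

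**Working it through.** **Reproducing the stated powers.** Inputs from 7.2: two measurements per unit, one-sided 5% level, null ICCs 0.82 and 0.875, and the five true ICCs. With θ = (1 + ICC)/(1 − ICC), the large-sample formula is

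power = Φ( √((N − 1)/4) × |ln(θ₀/θ₁)| − 1.645 ).

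For T1, 0.82 against 0.72, with N = 120: θ₀ = 1.82/0.18 = 10.111, θ₁ = 1.72/0.28 = 6.143, and ln(θ₀/θ₁) = 0.4983. Since √(119/4) = 5.454, the argument is 2.718 − 1.645 = 1.073 and the power is 0.858. In the same way:

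| | T1 0.72 | T1 0.70 | T2 0.775 | T2 0.80 | T2 0.815 |
|---|---|---|---|---|---|
| Stated in 7.2 | 0.858 | 0.935 | 0.969 | 0.873 | 0.749 |
| Formula, N = 120 | 0.8584 | 0.9349 | 0.9686 | 0.8731 | 0.7489 |
| Exact F test, N = 120 | 0.8575 | 0.9342 | 0.9680 | 0.8722 | 0.7477 |
| Exact F test, N = 60 | 0.603 | 0.716 | 0.793 | 0.622 | 0.491 |
| Exact F test, N = 30 | 0.375 | 0.460 | 0.528 | 0.388 | 0.303 |

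Only 120 units reproduce the stated values. A two-sided test at N = 120 does not (0.776 for the first).

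**Allowing for four locations per woman.** Let *share* be the part of the true between-location variance that lies between women. The documents do not give it, so it is varied from 0 to 1. Repeat errors are first taken as independent. The correlation between two location means in one woman is then r = 2 × share × ICC/(1 + ICC). The Satterthwaite degrees of freedom of the between-location mean square are

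df = [90(1 − r) + 29(1 + 3r)]² / [90(1 − r)² + 29(1 + 3r)²],

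and the number of independent units carrying the same information is 4/(2/df + 2/120). At ICC 0.82 and share 0.5, r = 0.4505, df = 73.8, and the 120 locations are worth 4/(0.0271 + 0.0167), about 91.

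The remaining rows below come from 2,000,000 draws of the mean-square ratio per cell. Power at a true 5% level means that the critical value has been reset so that the test really has 5% size at that share. The 95% level is assumed, since 7.3 gives none.

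| Share | 0 | 0.2 | 0.5 | 0.75 | 1.0 |
|---|---|---|---|---|---|
| Equivalent independent units (ICC 0.82) | 120 | 114 | 91 | 70 | 53 |
| T1 0.82 vs 0.72: power at a true 5% level | 0.858 | 0.844 | 0.771 | 0.666 | 0.535 |
| T1: rejection rate of the 120-unit test at true ICC 0.72 | 0.857 | 0.858 | 0.847 | 0.830 | 0.811 |
| T1: actual size of the 120-unit test | 0.050 | 0.057 | 0.086 | 0.127 | 0.175 |
| T1: coverage of the 120-unit 95% interval | 0.950 | 0.945 | 0.914 | 0.866 | 0.803 |
| T2 0.875 vs 0.815: power at a true 5% level | 0.748 | 0.730 | 0.643 | 0.533 | 0.413 |

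The 120-unit test keeps a rejection rate close to the stated power at moderate shares, but only because its size has risen above 5%.

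In the order of 7.2, the five powers at a true 5% level become 0.771, 0.872, 0.921, 0.782, 0.643 at share 0.5, and 0.535, 0.654, 0.718, 0.535, 0.413 at share 1.0. A separate simulation of full data sets (40,000 per setting) gave 0.768, 0.870, 0.919, 0.783, 0.639 and 0.539, 0.661, 0.717, 0.538, 0.413.

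**Shared measurement error.** If half the repeat error is also common to a woman's four locations (an assumption), T1 power at true ICC 0.72 is 0.752 / 0.731 / 0.661 / 0.572 / 0.465 across the same shares. The N = 30 values are reached only if true variance and error are both fully shared within a woman.

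**The case against.** The harm depends on a correlation the documents do not give. At share 0.2 it is negligible. At share 0.5 three of the five powers are still 0.78 or more, and the weakest was below 0.80 as stated. Share 1.0 would need all four locations in both breasts to have the same true value. This stands: the upper end is a bound and should not be read as a likely case. It does not rescue 7.2, which rests on the single value zero without saying so.

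Section 7.3 never says that the interval will use 120 units, and its reference to inter- and intra-subject variability is compatible with a nested model. This stands in part. What is shown for 7.3 is an unspecified method; the interval is too narrow only if the unit of 7.2 is carried over, which nothing in 7.3 prevents.

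Little rests on the test. It appears only in 7.2, no decision is tied to it, and a false rejection would understate MRF's reliability. Section 1.5 calls this a feasibility study, and section 2.1 sets out to "establish the T1 and T2 value baselines of normal glandular tissue". This also stands and limits the weight of the point. But 7.2 describes reliability as what it is sized for and draws the 30 women from these powers, and the interval is a planned result.

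Finally, power at a true 5% level assumes a critical value set with the share known, so it is not the power of a test one could run. That is correct, but the difference is small: a woman-level jackknife test at share 0.5 gives T1 power of about 0.75 at a size of about 0.06, against 0.771.

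**Conclusion.** The point holds and should be fixed. That the five powers rest on 120 independent units is established by exact reproduction, and no section adjusts for four locations per woman. The size of the error is known only as a range, under a model with a common woman effect and independent repeat errors: trivial at a share of 0.2 and material from about 0.5. At 0.5, T1 power falls from 0.858 to 0.771, the lowest T2 power from 0.749 to 0.643, and coverage of a 120-unit 95% interval to 0.914. If measurement error is also shared within a woman, the loss is greater. The consequences are overstated power behind the choice of 30 women and, if 120 units are used in the analysis, an ICC interval that is too narrow. The primary objective, the T1 and T2 baselines, does not rest on the ICC test.

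**What to change.** In 7.2, state that the five powers assume 120 independent locations. Replace them with power, or expected ICC interval width, for four locations in each of 30 women over a range of within-woman correlations. The N = 30 powers may be shown as a lower limit, but they are not the corrected values, because four locations per woman still add information.

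In 7.3, compute the ICC interval, and the one-sided test if it is kept, with the woman as the cluster. One option is a leave-one-woman-out jackknife on the Fisher z scale, centred on the mean of the 30 pseudo-values, with 29 degrees of freedom. In simulation (16,000 data sets per setting) its 95% coverage ranged from 0.938 to 0.952 and its one-sided size from 0.043 to 0.068. Any other woman-clustered method will do if its coverage is checked with 30 clusters. While 7.3 is open, two missing details can be added: the confidence level, and whether a systematic difference between the two scans in a phase counts as error (agreement) or not (consistency), with the matching estimator for both estimate and interval.

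The cost is wording and a short script, with no extra patients or scans. The stated power becomes less favourable. At ICC 0.82 the median 95% width is 0.123 if locations are independent and 0.141 at share 0.5, against 0.119 for the 120-unit interval. If locations really were independent, T1 power would be about 0.84 instead of 0.86.
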